## 6. Analysis Sets

### 6.1 Full Analysis Set

#### Full Analysis Set – Part A

The full analysis set – Part A (FAS – Part A) will include all randomized subjects in Part A. Subjects will be analyzed according to their randomized treatment group. Demographics, baseline disease characteristics, and efficacy analyses for Part A will be based on the FAS – Part A unless otherwise specified.

#### Full Analysis Set – Part B

The full analysis set – Part B (FAS – Part B) will include all randomized subjects in Part B. Subjects will be analyzed according to their randomized treatment group. Demographics, baseline disease characteristics, and efficacy analyses for Part B will be based on the FAS – Part B unless otherwise specified.

### 6.2 Safety Analysis Set

Subjects will be analyzed according to the actual treatment (defined in [Section 5.1](#)) in safety analysis for Part A and B respectively.

#### Safety Analysis Set – Part A

The safety analysis set for Part A, will consist of all randomized subjects who received at least one dose of investigational product in Part A.

#### Safety Analysis Set – Part B

The safety analysis set for Part B, will consist of all randomized subjects who received at least one dose of investigational product in Part B.

For Part B, no interim analyses will be performed.

## **7.2 Primary Analysis**

The primary analysis will occur when the primary completion date described in [Section 5.2](#) has been observed, and the data have been entered, cleaned, and locked. The objective for the primary analysis is to assess safety and efficacy through week 16 for Part A only.

## **7.3 Final Analysis**

The final analysis will occur when the end of study date described in [Section 5.2](#) has been observed, and the data have been entered, cleaned and locked. The final analysis will analyze efficacy and safety over the entire study period for Part A and Part B. For this, Part A and Part B will be analyzed separately.

## **8. Data Screening and Acceptance**

### **8.1 General Principles**

The objective of the data screening is to assess the quantity, quality, and statistical characteristics of the data relative to the requirements of the planned analyses.

### **8.2 Data Handling and Electronic Transfer of Data**

The Amgen Global Study Operations-Data Management (GSO-DM) department will provide all data to be used in the planned analyses.

### **8.3 Handling of Missing and Incomplete Data**

Subjects may be missing specific data points for a variety of reasons. In general, data may be missing due to a subject's early withdrawal from study, a missed visit, or inability to evaluate an endpoint at a particular point in time. The general procedures outlined below describe what will be done when a data point is missing.

#### **8.3.1 Missing Baseline Value**

Missing baseline evaluations will not be imputed.

#### **8.3.2 Missing Post-baseline Evaluation**

Refer to [Section 9.5.1.1](#) for handling of missing data for primary estimands defined in [Section 2.1](#).

**Secondary and exploratory endpoints will be included in descriptive summaries as observed without imputation for missing data. In analyses of secondary/exploratory endpoints involving statistical models detailed in [Section 9.5.2](#) and [Section 9.5.3](#), where endpoints cannot be derived due to missing IGA or EASI assessments, the missing binary endpoints (IGA 0/1, EASI50, EASI75,**

**EASI90) will be imputed using non-responder imputation (NRI). Missing binary endpoints that are not derived from IGA or EASI data (eg, Pruritus NRS  $\geq 2$ ) and missing continuous endpoints will not be imputed unless otherwise specified.**

Missing post-baseline safety data will not be imputed.

### 8.3.3 Missing and Incomplete Dates

For any listings, missing or incomplete dates will be listed as is.

For safety and concomitant medication tables, if any missing or incomplete date is reported, then, the following imputation rule will be used to impute the date.

	Missing	Imputation	Exception
Start Date	Day	Impute with 01	Default to Study Day 1 if an event starts the same year and month as Study Day 1 and the stop date is after Study Day 1
	Day and Month, or Month	Impute with 01 JAN	Default to Study Day 1 if an event started the same year as Study Day 1 and stop date is after Study Day 1
	Day, Month and Year	No imputation	
End Date	Day	Impute with minimum of last day of the month, EOS date	
	Day and Month, or Month	Impute with minimum of December 31 of the year, snapshot date for milestone analysis, EOS date	
	Day, Month and Year	No imputation	

If the imputed start date is after the end date, then the imputed start date will be defaulted to the end date.

If the imputed end date is before the start date, then the imputed end date will be defaulted to the start date.

For missing dates needed to calculate duration of atopic dermatitis, refer to [Section 5.3](#) for formulas to calculate duration.

#### **8.4 Detection of Bias**

This study has been designed to minimize potential bias using randomization of subjects into treatment groups and the use of blinding. Other factors that may bias the results of the study include:

- major protocol deviations likely to impact the analysis and interpretation of the efficacy endpoints
- subject level unblinding before final database lock and formal unblinding
- IP dosing non-compliance
- reasons for early withdrawal from treatment or from study

Important protocol deviations likely to impact the analysis and interpretation of the efficacy endpoints, **and would significantly affect subject's right, safety or wellbeing** will be tabulated **by treatment group** in the Clinical Study Report (CSR). Any unblinding of individual subjects prior to formal unblinding of the study will be documented in the CSR.

#### **8.5 Outliers**

Descriptive summaries will be examined to identify unexpected values.

Outliers due to data entry errors will be corrected by the study team before data lock. Outliers that are not due to data entry will be included in the analysis. If it is deemed necessary after the team reviews the output from the planned analyses after data lock, a post-hoc sensitivity analysis excluding subjects with outliers may be performed.

#### **8.6 Distributional Characteristics**

For categorical endpoints, descriptive summary will be provided. For continuous endpoints, normality will be assumed given the large sample size where central limit theorem applies.

#### **8.7 Validation of Statistical Analyses**

Programs will be developed, maintained, and output will be verified in accordance with current risk-based quality control procedures.

Tables, figures, and listings will be produced with validated standard macro programs where standard macros can produce the specified outputs.

The production environment for statistical analyses consists of Amgen-supported versions of statistical analysis software; for example, the SAS System version 9.4 or later.

## 9. Statistical Methods of Analysis

### 9.1 General Considerations

Subject disposition, demographics, and baseline disease characteristics will be summarized descriptively by randomized treatment group **using the FAS, by Part A and B respectively.**

**All efficacy analyses will be performed using the FAS by Part A and B respectively, unless stated otherwise. All safety analyses will be performed using safety analysis set, for Part A and B separately.**

For categorical endpoints, the descriptive statistics will contain frequency and percentage. For continuous endpoints, the descriptive statistics will include the number of observations, mean, standard deviation, 1st quartile, 3rd quartile, median, minimum, and maximum.

### 9.2 Subject Accountability

Subject disposition will be summarized descriptively for all randomized subjects, by randomized treatment group, **in Part A and B respectively.**

The disposition will include the number of subjects who are randomized, who are dosed with investigational product, **who discontinue IP including reasons of discontinuation**, who complete 16 weeks **of the study**, who complete 52 weeks **of the study**, who complete the whole study, and who withdraw prematurely including their reasons for withdrawal.

The disposition for **non-responders** will include the number of subjects **who switch to 420 mg SC Q2W**, who complete 52 weeks **of the study**, who complete the study, and who withdraw prematurely including their reasons for withdrawal.

### 9.3 Important Protocol Deviations

Important Protocol Deviations (IPDs) categories are defined by the study team before the first subject's initial visit and updated during the IPD reviews throughout the study prior to database lock. These definitions of IPD categories, subcategory codes, and descriptions will be used during the course of the study. Eligibility deviations are defined in the protocol.

### 9.4 Demographic and Baseline Characteristics

Demographic and baseline disease characteristics will be summarized by treatment group using descriptive statistics **based on FAS by Part A and B separately.**

Demographic information related to sex, age, race, region (Eastern EU which includes Czech Republic, Estonia, Hungary, Latvia, Poland, and Ukraine, Western EU which includes Germany, UK, Spain and Australia, North America including USA and Canada, Asia including South Korea and Japan), weight, height, and body mass index (BMI) will be presented by treatment group and overall. If multiple races have been reported for a subject, the subject will be categorized as multiple-race, as well as by combination of races.

A summary of baseline disease characteristics includes as follows:

1) Continuous variables to be summarized will include mean, standard deviation, 1st quartile, 3rd quartile, median, minimum, and maximum

- Screening total serum IgE level (kU/L)
- IGA
- EASI score
- SCORAD, PGI-S, EQ-5D-3L, EQ VAS Score, Pruritus NRS, POEM, DLQI
- Absolute eosinophil (cells/ $\mu$ L)
- Absolute neutrophil
- Basophil

2) Categorical variables to be summarized will include, the number and % of subjects in each category

- Screening total serum IgE level (< 150 kU/L vs.  $\geq$  150 kU/L)
- EASI score ( $\leq$  25 points vs. > 25 points)
- IGA (Category 3 vs. Category  $\geq$  4)
- Pruritus NRS (<4,  $\geq$ 4 and <7 vs.  $\geq$  7;  $\geq$ 2 vs <2,  $\geq$ 3 vs <3,  $\geq$ 4 vs. <4)
- POEM (0 to 2; 3 to 7; 8 to 16; 17 to 24; 25 to 28)
- S. aureus (positive vs. negative) (lesional and non-lesional skin separately)
- Age (18-35 years of age vs. 36-75 years of age)
- Gender (Male vs. Female)
- Race (White vs. non-White)
- Absolute eosinophil (< 300 cells/ $\mu$ L vs.  $\geq$  300 cells/ $\mu$ L)
- TCS use at Screening (Low Potency TCS vs. Medium to High Potency TCS vs. No TCS)
- Prior use of methotrexate (Yes vs No)
- Prior use of systemic immunosuppressants for AD (Yes vs No)

**Additional characteristics may be considered if scientific interest arises.**

**Medical history and AD history will be summarized by treatment group and for all subjects combined.**

## **9.5 Efficacy Analyses**

The multiplicity for analyses of primary estimands will be adjusted for tezepelumab 420 mg vs. placebo and 280 mg vs. placebo comparison using the method described in [Section 9.5.1.1](#). **For sensitivity analyses, subgroup analyses of primary estimands, and analyses of secondary/exploratory endpoints in Part A and B, significance testing, if performed, will be considered descriptive at a level of 0.05 (2-sided) with nominal p-values without adjustment for multiplicity.**

**When modeling odds ratio based on logistic regression in analyses described in [Section 9.5.1](#), [Section 9.5.2](#) and [Section 9.5.3](#), in case of sparse data in one or more particular treatment arm that results in convergence issues, logistic regression model adjusted by dichotomized baseline score ( $\leq$ median,  $>$ median) will be used. Odds ratio and associated 95% CI and p-value will be reported.**

**The following descriptive summaries will be provided by treatment at available time points using FAS and observed cases unless otherwise specified**

- **Categorical efficacy endpoints: frequency/percentage.**
- **Continuous efficacy endpoints and associated changes from baseline: mean, standard deviation, median, 1st quartile, 3rd quartile, minimum, and maximum.**

**The above analyses will be performed using FAS-Part A by truncating the observations collected after switching to 420 mg SC Q2W for EASI-50 non-responders, and will be repeated using Switcher Analysis Set.**

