Depending on whether subjects are randomized to Q2W or Q4W dosing, the dose at week 2, **week 6, week 10 and so on**, could be placebo or tezepelumab. Non-responders are defined as those subjects who have not achieved at least a 50% improvement in EASI at week 16 compared to baseline (day 1). Subjects who are determined to be non-responders in Part A will receive tezepelumab 420 mg SC Q2W for the remainder of the study, beginning with the week 18 dose. The randomized treatment assignments for the non-responders will remain blinded until the end of study.

Part B is a randomized, placebo-controlled, double-blind **proof-of-concept** study designed to evaluate the safety and efficacy of tezepelumab when administered with moderate class TCS in adults with moderate-to-severe AD. Enrollment of subjects in Part B of the study will only commence if there is a result of “not futile” for the first interim analysis in Part A **and Part A has completed enrollment of 240 subjects**. Following the screening period, eligible subjects will be randomized 2:1 to receive 420 mg SC

Q2W or placebo; both groups in Part B will be allowed to use TCS after the day 1 visit. Non-responders in Part B will not be switched to 420 mg SC Q2W at week 18 and will remain on their initial dose for the duration of the study.

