## 5.6 Secondary/Exploratory Endpoints – IGA 0/1 and EASI 50/75/90

Secondary endpoints, EASI 50 and EASI 90 at week 16 in Part A, and Exploratory endpoints, IGA 0/1 at week 24, week 36 and week 52 in Part A and B, and IGA 0/1 at week 16 in Part B, will be defined in the same way as primary endpoints in [Section 5.5](#). For example, the time point of interest is week 24, week 36 and week 52 instead of week 16, the use of TCS/TCI will be considered from day 29, to week 24, week 36 and week 52 respectively.

Time-to-event analysis of EASI 50/75/90 will be handled as described in [Section 9.5.2](#) and [Section 9.5.3](#).

In addition, IGA 0/1 and EASI 75 at time points other than week 16, week 24, week 36 and week 52 in both Part A and B will be defined in the same way as primary endpoints in [Section 5.5](#) at corresponding time points. For example, when the time point of interest is week 4, week 6, week 8, week 10, and week 12 instead of week 16, the use of TCS/TCI will be considered from day 29, to those time points respectively.

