### **9.5.1 Analyses of Primary Efficacy Endpoint(s)**

#### **9.5.1.1 Primary Analysis of the Primary Endpoints**

[figure not shown]
The primary analysis of the primary estimands as defined in [Section 2.1](#) will be performed using the FAS – Part A. Primary endpoints are defined in [Section 5.5](#). **Where an endpoint cannot be derived due to missing IGA or EASI assessments, a patient will be assumed not to have achieved the outcome, that is, Non-Responder Imputation (NRI).**

Treatment effect **for IGA 0/1 at week 16** will be tested using a logistic regression model with baseline IGA as covariate. **Similarly, treatment effect for EASI 75 at week 16 will**

**be tested using a logistic regression model with baseline EASI as covariate.** From **each** model, odds ratio and 95% CIs will be reported, comparing each tezepelumab dose group to placebo.

To control the family-wise type 1 error rate at 0.05 (**2-sided**) for the multiple comparisons of 420 mg vs. placebo and 280 mg vs. placebo, the hypotheses **described in Section 2.2** will be tested using a Bonferroni-based gatekeeping chain procedure (**Dmitrienko 2013**) as shown in [Figure 9-1](#). This procedure will split alpha of 0.05 equally to test in parallel tezepelumab 420 mg SC Q2W versus placebo and tezepelumab 280 mg SC Q2W versus placebo for IGA 0/1 and EASI 75 sequentially within each parallel **dose** path. If one of the parallel **dose** paths rejects **the 2** hypotheses sequentially, and the other **dose** path has at least one hypothesis not rejected, then the unspent  $\alpha$  of 0.025 from the successful path will be propagated to the **unsuccessful dose path** to retest the 2 hypotheses sequentially at a level of 0.05.

Figure 9-1. Alpha Split Between Two Doses of Interest

In addition, analysis of primary endpoints may be considered using mFAS-Part A as a supporting analysis to examine the impact of COVID-19 2020 outbreak on outcomes without multiplicity adjustment.

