#### 9.5.1.3 Subgroup Analyses of Primary Endpoints

The consistency of the detected overall treatment effect on the primary endpoints will be explored for Part A only. A logistic regression model will include baseline IGA or EASI, the subgroup being tested, treatment, and treatment by subgroup interaction. The odds ratio will be calculated for each category of subgroup populations. The subgroups mentioned in [Section 4.2](#), will be used in this subgroup analyses.

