#### 9.5.2 Analyses of Secondary Efficacy Endpoint(s)

The secondary estimands will be analyzed using **FAS – Part A**. Secondary endpoints are defined in [Section 5.6](#).

For the binary endpoint, EASI 50/90 at week 16, the treatment effect will be **analyzed** using a logistic regression model adjusting for baseline EASI. From this model, odds ratio and 95% CIs will be reported comparing each tezepelumab dose group to placebo.

The time to achieving EASI 50/75/90 response prior to switching to tezepelumab 420 mg Q2W will be summarized by Kaplan-Meier (KM) curves, the number of subjects achieving EASI 50/75/90 and the number of subjects censored will be provided at available time points. Subjects who do not achieve EASI 50/75/90 will be censored at the date when formal assessments of non-responder (as defined in protocol, that is, not achieve at least 50% improvement in EASI at week 16

compared to baseline) are recorded or end of study date, whichever is the earliest. Subjects who receive rescue medication from day 29 will be censored at the point when subjects receive rescue medication.

The treatment effect for change from baseline in SCORAD and Pruritus NRS each at week 16 will be analyzed using a **Mixed Model for Repeated Measures (MMRM)**. The model for change from baseline in SCORAD at week 16 will include visit and baseline SCORAD as covariates and an interaction term between arm and visit. The model for change from baseline in Pruritus NRS at week 16 will include visit and baseline Pruritus NRS as covariates and an interaction term between arm and visit. **AR(1) variance-covariance structure will be used.** Least square means and corresponding 95% CI will be calculated for each treatment group and for the difference between treatment groups.

Serum concentration will be summarized descriptively by treatment group for each sampling time point using the PK analysis set.

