#### *Part B*

The analysis of exploratory endpoints for Part B will be performed using the **FAS – Part B**. The methods of analyses of exploratory endpoints for Part B will be the same as the analysis of exploratory endpoints for Part A. In addition, Bayesian methods may be used to borrow historical control data in estimating treatment effect, in addition to using observed data from the current study.

The time to achieving EASI 50/75/90 response prior to switching to tezepelumab 420 mg Q2W will be summarized by Kaplan-Meier (KM) curves, the number of subjects achieving EASI 50/75/90 and the number of subjects censored will be provided at available time points. Subjects who do not achieve EASI 50/75/90 will be censored at the date when formal assessments of non-responder (as defined in protocol, that is, not achieve at least 50% improvement in EASI at week 16 compared to baseline) are recorded or end of study date, whichever is the earliest. Subjects who receive rescue medication from day 29 will be censored at the point when subjects receive rescue medication.

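### The sparse-arm fallback in SAP 9.5 recodes baseline, which cannot give a finite odds ratio when a compared arm has no responders or only responders; the test and CI type are not named

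*SAP*

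**What the plan says.** SAP 9.5 sets one rule for every logistic analysis in 9.5.1, 9.5.2 and 9.5.3. It reads that "in case of sparse data in one or more particular treatment arm that results in convergence issues, logistic regression model adjusted by dichotomized baseline score" (split at the median) will be used. It then promises a full set of results: "Odds ratio and associated 95% CI and p-value will be reported". Neither the treatment term nor the estimation method changes.

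The analyses under this rule are:

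- **Part A primary endpoints (9.5.1.1):** "odds ratio and 95% CIs will be reported, comparing each tezepelumab dose group to placebo".
- **Subgroups (9.5.1.3):** one model with a treatment-by-subgroup interaction. "The odds ratio will be calculated for each category of subgroup populations".
- **EASI 50 and EASI 90 at week 16 (9.5.2):** analysed "using a logistic regression model adjusting for baseline EASI".
- **Part B (9.5.3.1):** "The methods of analyses of exploratory endpoints for Part B will be the same as the analysis of exploratory endpoints for Part A". SAP 3.2 gives Part B 40 tezepelumab and 20 placebo subjects.

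Neither these sections nor Protocol 10.3.2.2 says whether tests are Wald, score or likelihood-ratio, or whether intervals are Wald or profile-likelihood. No exact or penalised method is mentioned.

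**The concern.** The trigger and the remedy concern different parts of the model. The trigger is sparseness in a treatment arm; the remedy simplifies the baseline covariate. A common way for a sparse arm to stop a logistic fit is to contain no responders, and then the treatment coefficient has no finite estimate. The fallback would be invoked and would fail in the same way, while the SAP still commits to an odds ratio, interval and p-value.

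Because the test is not named, the analyst would have to choose a method after seeing an empty arm, and the candidate methods can disagree widely on the same data. Non-responder imputation for missing IGA and EASI assessments, and counting TCS/TCI rescue as non-response, both push responder counts down.

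**Working it through.** **1. The plan's own figures.** The documents give no figure for the fallback. The nearest is the power in SAP 3.2: at least 85% per endpoint, with 60 per arm, 10% dropout, two-sided 0.025, and rates of 10% v 40% (IGA 0/1) and 15% v 50% (EASI 75). With n = 54 per arm, power = Φ{(d√n − 2.241√(2p̄(1−p̄))) / √(p₁(1−p₁)+p₂(1−p₂))}:

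- IGA 0/1: (2.204 − 1.373)/0.574 = 1.45, giving 92.6%.
- EASI 75: (2.572 − 1.485)/0.614 = 1.77, giving 96.2%.

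The stated power stands. This point is not about sample size.

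**2. Recoding baseline does not help.** The documents give no baseline data, so baseline values were simulated. The table shows maximum-likelihood fits with median-split baseline, by number of iterations.

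| Data | Iterations | log OR | SE | Wald p |
|---|---|---|---|---|
| 24/60 v 0/60 | 5 | 5.80 | 2.88 | 0.044 |
| 24/60 v 0/60 | 25 | 25.81 | 63,100 | 0.9997 |
| 8/40 v 0/20 | 5 | 4.78 | 4.97 | 0.336 |
| 8/40 v 0/20 | 25 | 24.78 | 109,000 | 0.9998 |

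The log odds ratio rises by 1 per iteration without limit, so the output depends on when the software stops. Continuous baseline behaves the same way. With 1/60 placebo responders both codings converge (OR 38.7 continuous, 39.9 median split), so the fallback is not needed there.

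**3. The unnamed test matters.** The unadjusted likelihood-ratio statistic is G² = 2[ℓ(arm 1) + ℓ(arm 2) − ℓ(pooled)], and an empty arm contributes ℓ = 0. For 8/40 v 0/20, ℓ(8/40) = 8 ln 0.2 + 32 ln 0.8 = −20.02 and ℓ(8/60) = −23.56. So G² = 7.09 and p = 0.008.

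| Active v 0/20 | Wald p | Likelihood-ratio p |
|---|---|---|
| 4/40 | tends to 1 | 0.066 |
| 8/40 | tends to 1 | 0.008 |
| 16/40 | tends to 1 | 0.00007 |

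For 16/40 v 0/20 the profile-likelihood interval runs from about 6.0 to infinity, while the Wald interval is in effect 0 to infinity.

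**4. Size of the ordinary likelihood-ratio test.** Exact binomial enumeration under a common rate, without baseline adjustment:

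| Arms, rate, nominal level | Likelihood-ratio | Firth penalised likelihood-ratio |
|---|---|---|
| 40 v 20, 10%, 5% | 7.4% | 3.5% |
| 60 v 60, 3%, 5% | 9.2% | 1.2% |
| 60 v 60, 10%, 2.5% | 3.2% | 2.2% |

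In the last setting the Wald test rejects 0.8% of the time.

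**5. Chance of no placebo responder, (1 − p)ⁿ.**

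- Part A primary, n = 60, plan's rates: 0.9⁶⁰ = 0.18% (IGA 0/1); 0.85⁶⁰ = 0.006% (EASI 75).
- Part B, n = 20: 0.9²⁰ = 12%; 0.85²⁰ = 3.9%; 0.8²⁰ = 1.2%; 0.95²⁰ = 36%. No Part B placebo rate is stated. The 20% half-width in SAP 3.2 does not fix one: for IGA 0/1, 8% v 38% gives 19.2% and 10% v 40% gives 20.1%.
- IGA 0/1 subgroup category at 10%, assumed 30, 20 or 15 placebo subjects: 4.2%, 12%, 21%.
- EASI 90, n = 60, assumed rate 2%, 5% or 8%: 30%, 4.6%, 0.7%.

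The Part B rate could move either way. It could rise because "both groups in Part B will be allowed to use TCS after the day 1 visit". It could fall because "IGA 0/1 at week 16 in Part B, will be defined in the same way as primary endpoints", if TCS/TCI use counts as non-response. SAP 5.5 speaks of rescue use, SAP 5.6 of use, and Protocol 7.1.5 separates permitted Part B TCS from rescue, so the direction is uncertain.

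**6. What a penalised fit gives.** Without covariates, Firth adds 0.5 to each cell. For 16/40 v 0/20, OR = (16.5/24.5)/(0.5/20.5) = 27.6. Adjusted for simulated continuous baselines, the median was OR 27, profile CI 3.3 to 3,500 and penalised likelihood-ratio p 0.0004. Fisher's exact p is 0.0005.

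**The case against.** The strongest case against is that little depends on this rule. SAP 9.5 treats tests outside the Part A primary comparisons as descriptive, nominal and only if performed, and Part B tests no hypothesis. Response percentages by arm are planned, so 0/20 v 16/40 would be plain to any reader. Protocol 10.3.2.2 adds a difference in percentages with a 95% CI for the primary endpoints, and Part B may borrow historical controls by Bayesian methods. Where data are not sparse the choice of test hardly matters: 24/60 v 6/60 gives Wald p 0.0004 and likelihood-ratio p 0.0001. All of this stands and limits the severity. It does not repair a rule that promises results its model cannot supply.

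Four stronger readings are tempting and not supported:

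- **That the Part A primary tests are at real risk.** At the plan's own rates an empty placebo arm is very unlikely. An empty 210 mg arm alone leaves the 420 mg and 280 mg odds ratios unchanged under the standard model.
- **That the likelihood-ratio test is a safe answer.** It stays computable, but step 4 shows it is liberal here. The small p-values in step 3 are therefore optimistic.
- **That the choice always swings p from near 1 to below 0.001.** That needs a large effect; 4/40 v 0/20 gives 0.066.
- **That the median split is useless.** It can help when sparseness in the baseline covariate causes the failure.

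The larger probabilities (EASI 90, subgroups, Part B at 5%) rest on assumed rates or sizes.

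**Conclusion.** The point holds as a minor one. With zero or all responders in a compared arm, or in an arm within a subgroup category, the stated fallback cannot yield a finite maximum-likelihood odds ratio, and the SAP leaves the test and CI type open. The failure itself is algebraic and needs no assumption. How often it would occur depends on response rates that the documents give only for IGA 0/1 and EASI 75 in Part A. There the risk is remote. In Part B it is about 4% to 12% if the Part A placebo rates of 15% and 10% carried over, which the documents do not say. The size calculations are unadjusted for baseline, and the refits use simulated baselines unrelated to response.

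**What to change.** Replace the fallback sentence in SAP 9.5 with:

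> If either arm of a comparison (or either arm within a subgroup category) has zero responders or all responders, that odds ratio will be estimated by Firth penalised likelihood with the original baseline covariate, fitted to the two arms being compared (within the subgroup category for subgroup analyses), with a profile penalised-likelihood 95% CI and a penalised likelihood-ratio p-value. If the placebo arm is the empty arm, this applies to every dose comparison; if only one dose arm is empty, the other comparisons keep the standard model. The median split will be used only if non-convergence is due to the baseline covariate.

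In SAP 9.5.1.1, name the test and the matching CI type for the standard model, choosing one whose size holds at the 0.025 level. Do not default to the ordinary likelihood-ratio test, which rejects 3.2% of the time at nominal 2.5% (60 v 60, 10% common rate, unadjusted).

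The cost is a short SAP edit and a standard software option. There are downsides. The estimator depends on the data once triggered, the odds ratio is shrunk, and the upper confidence limit stays very wide, so mainly the lower limit informs. An affected subgroup category would be estimated outside the shared interaction model, which its table should footnote.
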